## 3. STUDY DESIGN

### 3.1 Study Design

This study is a Phase 2, multicenter, randomized, double-blind, placebo-controlled study to evaluate the efficacy and safety of imsidolimab in adult subjects with hidradenitis suppurativa (HS). This study will also characterize the pharmacokinetic (PK) profile of imsidolimab and explore the immune response to imsidolimab in subjects with HS.

To be eligible for this study, subjects must have a clinically confirmed diagnosis of HS with a disease duration of at least 6 months before Day 1. In addition, subjects will have the following characteristics at Screening and Day 1:

- 1) HS lesions present in at least 2 distinct anatomical areas, 1 of which must be Hurley Stage II (i.e., single or multiple, widely separated, recurrent abscesses with tract formation and cicatrization) or Hurley Stage III (i.e., diffuse or near diffuse involvement, or multiple interconnected tracts and abscesses across the entire area);
- 2) total abscess and inflammatory nodule (AN) count of  $\geq 5$ ;
- 3)  $\leq 20$  draining fistulas.

Randomization will be stratified based on Hurley Stage at baseline (Stage II or III).

The maximum study duration per subject is approximately 44 weeks, which includes a screening period of up to 30 days, followed by a 16-week placebo-controlled period, a 16-week treatment extension period, and an 8-week follow up period. The placebo-controlled period ends at Day 113 (Week 16) and the treatment extension period starts when study treatment is administered at the Week 16 visit. Of note, during the extension period all subjects will receive imsidolimab but their treatment will remain blinded.

During the placebo-controlled period, eligible subjects will be randomized (1:1:1) to receive either imsidolimab (at 1 of 2 different regimens) or placebo, subcutaneously (SC) administered on 4 occasions: Day 1, Day 29 (Week 4), Day 57 (Week 8), and Day 85 (Week 12).

The treatment arms during the placebo-controlled period will be as follows:

[figure not shown]
- Imsidolimab 400 mg on Day 1, followed by 200 mg on Days 29, 57, and 85
- Imsidolimab 200 mg on Day 1, followed by 100 mg on Days 29, 57, and 85
- Placebo on Days 1, 29, 57, and 85

During the extension period, all subjects will receive imsidolimab, SC administered on 4 occasions:

- 400 mg dose of imsidolimab on Day 113 for subjects assigned to placebo arm 3A during the placebo-controlled period, followed by 200 mg doses on Days 141, 169, and 197

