**Figure 1 Study Schema**

Abbreviations: D, day; SC, subcutaneously; W, week.

a During the placebo-controlled period, subjects will be randomized (1:1:1) to receive either imsidolimab (at 1 of 2 different regimens) or placebo, SC administered on 4 occasions: 1) 400-mg dose of imsidolimab on Day 1, 200-mg dose of imsidolimab on Days 29, 57, and 85; 2) 200-mg dose of imsidolimab on Day 1, 100-mg dose of imsidolimab on Days 29, 57, and 85.

b The placebo-controlled period ends on Day 113 (week 16) visit, before study treatment administration. Pre-dose assessments performed on Day 113 (week 16) will be used to evaluate the primary and secondary efficacy endpoints, as well as the safety, tolerability, and immune response of imsidolimab compared with placebo. The extension period starts when the study treatment is administered on Day 113 (week 16) visit. All subjects will receive imsidolimab SC administered on 4 occasions during the extension period.

c Subjects in Arm 3 randomized to placebo during the placebo-controlled period will be randomized 1:1 to receive either a 400-mg dose of imsidolimab on Day 113, followed by a 200-mg dose on Days 141, 169, and 197; or a 200-mg dose of imsidolimab on Day 113, followed by a 100-mg dose of imsidolimab on Days 141, 169, and 197. Subjects randomized to imsidolimab in Arms 1 and 2 during the placebo-controlled period will continue to receive the same maintenance dose of imsidolimab (200 mg or 100 mg) on Days 113, 141, 169, and 197.

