### 6.6.1 Study Day and Visit Window Definitions

Adverse Events will be closely monitored on each patient throughout their participation in the study. Adverse Events will be reported by the study period that they occurred in as detailed in the Data Handling Rules Appendix. Safety assessments for other safety variables will occur as detailed in the Schedule of Activities in **Section 3.6**. Safety data assessed per the Schedule of Activities will be allocated according to the rules for efficacy data in **Section 6.2.1**.

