### 6.6.3 Adverse Events

AEs experienced by the subjects will be collected throughout the entire study and will be coded using the latest version of the MedDRA specified in the approved Data Management Plan. Analysis of adverse events will be carried out on the Safety Analysis Set during the placebo controlled period and the Extension Analysis Set for the extension period.

An adverse event is considered treatment-emergent if the date of onset is during or after first dose of study treatment, or if the AE present at baseline that worsens in either intensity or frequency after first dose of study treatment. An adverse event that begins on the same date as the first dose of study treatment is treatment-emergent if the AE begins on or after the time of first dose or if the time of AE onset is unknown.

The severity of AEs will be evaluated as “Mild”, “Moderate”, and “Severe” using the criteria specified in [Section 8.2.1.3.1](#) of the study protocol.

AEs will be classified as related, possibly related, unlikely to be related, or unrelated to study treatment using the criteria specified in [Section 8.2.1.3.2](#) of the study protocol.

Adverse events will be categorized as serious or non-serious using the definition specified in [Section 8.2.1.2](#) of the study protocol.

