## APPENDIX 1 DATA HANDLING RULES

The following table presents the algorithms to be used in SAS to calculate the derived variables, including rules for handling other missing data or partial dates, or irregular/unexpected data issues.

Category	Description	Data Handling Rules
1. Medical History	Medical History Beginning Date of Condition	
 
Missing day of begin date of condition will be imputed as the 1st of the month for the purpose of computing the onset day.
 
Missing month of begin date of condition will be imputed as June for the purpose of computing the onset day
 

	Medical History End Date of Condition	
 
Missing day of end date of condition will be imputed as the 30th of the month for the purpose of computing the onset day.
 
Missing month of end date of condition will be imputed as June for the purpose of computing the onset day
 

2. First and Last Treatment Dates	date/time of first and last dose of a study treatment	The date and time (24 hr. clock) of the first dose of study treatment will be taken from the Dosing eCRF. The date of the last dose of study treatment will be the last date of dosing from the Dosing eCRF for the treatment.
3. Last Visit Date	Date of Last Visit	Date of last visit according to the Visit eCRF.
4. Last Study Participation Date (SDTM variable, typically named RFPENDTC)	Last Study Participation Date (SDTM variable, RFPENDTC), where SDTM denotes Study Data Tabulation Model	Last study participation date is defined as last known date of contact which would be the later of the following dates: last visit date, date of the last dose, date of study completion or discontinuation, or death date.
5. Study Day Definitions	Study Day for assessment/event which occurs on or after the start of study treatment	Study Day = Date of assessment/event – date of the first dose of study treatment + 1.
	Study Day for assessments/events on days prior to the first dose of study treatment in the study	Study Day = date of assessment/event – first dose date of treatment in the study.
	Study Day of Randomization	Study Day of Randomization = date of randomization – date of the first dose of study treatment in the study + 1. Study Day is 1 if baseline day is on the day of randomization.

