8. Adverse event	Treatment-emergent adverse event	
If the AE start date is partial/missing, then
 
 
If AE start date is completely missing, then the AE is considered as treatment-emergent.
 
If both AE start month and day are missing and AE start year is the same or after the first dose year, then the AE is considered as treatment-emergent.
 
If AE start day is missing and AE start year and month are the same or after the first dose year and month, then the AE is considered as treatment-emergent.
 

Category	Description	Data Handling Rules
		Missing/incomplete (partial) AE start and end dates will not be imputed for data listings.
	Assignment of TEAE to Placebo-Controlled vs. Extension and Follow Up Period	Report the TEAE in placebo-controlled period if AP01SDT < AESTDTC; Else report the TEAE in extension and follow-up period if AP02SDT < AESTDTC
	Missing relationship to study drug	For TEAE summary by relationship, a TEAE with a missing relationship to study drug will be considered as related.
9. Efficacy	Change from baseline	Endpoint value at Week x – endpoint value at baseline
	Percent change from baseline	(Endpoint value at Week x – endpoint value at baseline)/ endpoint value at baseline
	Scoring rules for DLQI questionnaires	
 
• If one question left unanswered, assign a score of 0 for that question.
 
• If two or more questions are left unanswered the questionnaire is not scored.
 
• For question 7, 
 
◦ “Yes” is assigned a score of 3
 
◦ “Not Relevant” is assigned a score of 0
 
◦ “No” and “A lot” is assigned a score of 2
 
◦ “No” and “A little” is assigned a score of 1
 
 
 

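### The SAP's rule for assigning TEAEs to study periods has no upper bound, so, read with period start dates, it leaves the extension TEAE tables empty and puts post-crossover events in the placebo-controlled period

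*SAP*

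**What the plan says.** SAP Appendix 1 (Data Handling Rules), item 8, gives the only rule for placing a TEAE in a study period: "Report the TEAE in placebo-controlled period if AP01SDT < AESTDTC; Else report the TEAE in extension and follow-up period if AP02SDT < AESTDTC".

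The SAP treats this as the working specification. The appendix opens with "The following table presents the algorithms to be used in SAS to calculate the derived variables", and Section 6.6.1 sends the reader there: "Adverse Events will be reported by the study period that they occurred in as detailed in the Data Handling Rules Appendix". Other safety data follow a different route: "Safety data assessed per the Schedule of Activities will be allocated according to the rules for efficacy data".

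The period boundary is stated clearly elsewhere. Section 3.1 says that "the treatment extension period starts when study treatment is administered at the Week 16 visit", and the Figure 1 footnote says "The placebo-controlled period ends on Day 113 (week 16) visit, before study treatment administration". Section 6.6.3 then plans the AE analysis on the "Safety Analysis Set during the placebo controlled period and the Extension Analysis Set for the extension period", and Section 7.9 repeats that split for all safety analyses.

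Neither document defines AP01SDT or AP02SDT. Item 2 of the same appendix says "The date and time (24 hr. clock) of the first dose of study treatment will be taken from the Dosing eCRF", so dose times are available, but item 8 does not say whether they are used.

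**The concern.** The rule reads as IF/ELSE. The first condition asks only whether onset is later than AP01SDT; it does not also require onset to be before AP02SDT. If the two variables are period start dates, an event in Week 30 is later than both. It satisfies the first condition and is labelled placebo-controlled, and the second condition is never evaluated for it.

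Two required outputs would then be wrong. The extension TEAE tables on the Extension Analysis Set would contain no events. The placebo-controlled TEAE tables would cover up to 40 weeks in every arm instead of 16, over the Safety Analysis Set denominator (Protocol 9.4.8.1).

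The second error matters more, because all placebo subjects who continue receive imsidolimab from Day 113. No text states which treatment column takes an event that starts on imsidolimab after crossover but carries a placebo-controlled flag. SAP 5.2 deals with subjects given both treatments within the placebo-controlled period, SAP 3.2 with subjects given the wrong treatment, and the table shells are in a separate document. My inference, not something the documents state, is that such events would most likely be counted under placebo. If the drug raises AE risk, that would pull the randomised comparison toward no difference.

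**Working it through.** The SAP gives no figure for this rule, so there is none to reproduce. The check is logical, followed by a count of days.

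**Inputs**
- Rule: SAP Appendix 1, item 8, taken literally with strict inequalities.
- AP01SDT = Day 1 and AP02SDT = Day 113 (assumed to be the period start dates; nominal days from the Schedule of Activities).
- Last planned visit Day 281; extension to Day 225 (Week 32); follow-up Days 226 to 281.
- Visit windows: Day 113 ±4, Day 281 ±5.
- 40 subjects per arm randomised, 36 expected to remain at Week 16 (SAP 3.5).

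**Logic**
1. The ELSE branch is reached only if AP01SDT < onset is false, that is, onset ≤ AP01SDT.
2. The ELSE branch then requires AP02SDT < onset.
3. Together: AP02SDT < onset ≤ AP01SDT, so AP02SDT < AP01SDT.
4. This is impossible for any non-missing pair with AP01SDT ≤ AP02SDT. The extension branch is unreachable whatever the actual dates.

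Replacing < with ≤ does not rescue it: step 3 becomes AP02SDT ≤ onset < AP01SDT, which is equally impossible.

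**Day count, dates only, onset Days 1 to 281**

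| Period assigned | Rule as written | Bounded rule* |
|---|---|---|
| Placebo-controlled | 280 (Days 2–281) | 112 (Days 1–112) |
| Extension/follow-up | 0 | 169 (Days 113–281) |
| Neither | 1 (Day 1) | 0 |

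*Placebo-controlled if AP01SDT ≤ onset < AP02SDT; extension/follow-up if onset ≥ AP02SDT.

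Moving AP02SDT to Day 109 or Day 117 leaves the as-written column unchanged.

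**Misassigned days**
- Onsets dated after the Week 16 dose: 281 − 113 = 168 days; 168/280 = 60%.
- Split: 225 − 113 = 112 in the extension and 281 − 225 = 56 in follow-up.
- Range over the visit windows: 276 − 117 = 159 to 286 − 109 = 177 days.
- Post-dose onsets on Day 113 itself are also misplaced; pre-dose onsets that day are placed correctly.

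**Subjects exposed to the error**
On the planned numbers, 36 of 40 placebo subjects and 3 × 36 = 108 of 120 overall remain at Week 16. If all of them enter the extension, their later TEAEs are the ones affected.

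**Smaller gaps in the same line**
- On dates alone, an onset on the first-dose date fails the first test and, with AP02SDT present, the second. Section 6.6.3 can nevertheless count it as treatment-emergent.
- Partial and missing onset dates are handled for TEAE status only, not for period. A completely missing date is declared treatment-emergent, but where missing values rank lowest, as in SAS, it satisfies neither test.
- An AE that begins before dosing and worsens afterwards is a TEAE but fails both tests if it keeps its original onset date. This mainly concerns AEs that begin between consent and Day 1.

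**The case against.** The best defence is that the intent is plain. Section 6.6.1 says AEs are reported by the period in which they occurred, the design sections fix the boundary at the Week 16 dose, and the Introduction describes the SAP as guidelines that allow justified departures. Dry runs and programming QC are planned, and extension TEAE tables with no events would be hard to miss. AE summaries are descriptive, with no planned test.

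Part of this stands. The error may well be noticed. The placebo-column effect depends on shells that are not in these documents, and SAP 5.2 and 5.3 say that subjects are analysed as treated, although neither settles the column for a post-crossover event. The 60% is a share of possible onset days, not of events or subjects. A missing AP02SDT (no extension dose) is a minor matter, because the first test already places every onset after Day 1. Date-only comparison is an assumption, since item 2 records the time of first dose.

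The core does not yield. Correct output would require the programmer to depart from the text labelled as the algorithm. If empty tables prompt a correction, the handling of same-day, partial and missing dates would be chosen without a written rule, possibly after unblinding. Nor do other readings of the variables help: if AP01SDT were the end of the first period, events after that end would be labelled placebo-controlled.

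**Conclusion.** The concern holds. As written, and for any AP01SDT on or before a non-missing AP02SDT, every TEAE dated after the first-dose date goes to the placebo-controlled period and none goes to extension/follow-up. This contradicts the SAP's own period boundary and its by-period AE analyses. On the planned schedule, 168 of the 280 assigned onset days (60%; range 159 to 177 days over the visit windows) are misplaced.

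The conclusion rests on reading the two undefined variables as ordered period start dates. The size of any dilution of the imsidolimab–placebo AE contrast cannot be derived from the documents, and none is claimed.

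The main effect is on the final analysis. At the Week 16 primary analysis it is limited to extension events recorded by the data cut-off in subjects enrolled early. Safety is a secondary objective, and the rule spoils the only randomised AE comparison, so it must be corrected even though the slip is simple.

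**What to change.** Replace the line in Appendix 1, item 8, and add the missing definitions:

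1. Define AP01SDT and AP02SDT as the date/time of the first dose in the placebo-controlled and extension periods.
2. If AP02SDT is non-missing and onset is on or after AP02SDT (using time when known), assign to extension/follow-up. Otherwise, if onset is on or after AP01SDT, assign to placebo-controlled.
3. State one convention, identical in all arms, for same-day onsets with unknown time and for partial or missing onset dates.
4. Assign pre-dose events that worsen after dosing by the date of worsening; Protocol 8.2.1.4 already requires changes in severity to be documented.
5. State which treatment column is used in each period's TEAE tables.

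Reordering the tests alone is not enough. With the strict inequality kept and dates only, Day 1 onsets would still have no period and all Day 113 onsets would count as placebo-controlled.

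The cost is a few lines of SAP text and derivation code, with no operational cost.

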#### Events with Partial Onset Dates

All treatment-emergent adverse events (TEAEs) will be included in the tabulations regardless of the completeness of the onset dates. Partial dates will be imputed in order to determine if an AE is treatment-emergent using the imputation rules in [Appendix 1](#); however, imputed dates will not be provided in the data listings.

**Uncoded Events:** Before the database lock, uncoded events will be assigned the string “UNCODED” as the body system, and the verbatim term will be used as the preferred term, so they can be included in the summary tables. In the final dataset, all the adverse events will have been coded.

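### The SAP's period rule for TEAEs leaves some events in neither period: first-dose-date onsets if compared by date, undated events, and baseline events that worsen

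*SAP*

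**What the plan says.** SAP Appendix 1 presents its table as the algorithms to be programmed. Item 8 assigns TEAEs to periods with two tests in sequence: "Report the TEAE in placebo-controlled period if AP01SDT < AESTDTC", then "Else report the TEAE in extension and follow-up period if AP02SDT < AESTDTC". It does not define AP01SDT or AP02SDT, and it does not say whether the comparison is by date or by date and time.

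Other parts of the SAP settle which events are TEAEs:

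- **First-dose date.** SAP 6.6.3 makes an AE that starts on the first-dose date "treatment-emergent if the AE begins on or after the time of first dose or if the time of AE onset is unknown".
- **Worsening.** The same section counts an AE present at baseline as a TEAE if its intensity or frequency worsens after the first dose.
- **No start date.** Appendix 1, item 8: "If AE start date is completely missing, then the AE is considered as treatment-emergent".
- **Incomplete dates.** SAP 6.6.3, Events with Partial Onset Dates, says all TEAEs "will be included in the tabulations regardless of the completeness of the onset dates". It adds: "Partial dates will be imputed in order to determine if an AE is treatment-emergent using the imputation rules in" Appendix 1. The rules found there decide only whether an event is treatment-emergent. They supply no substitute date and no default period.

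The period rule drives the tables. SAP 6.6.1 sends AE reporting by period to Appendix 1. SAP 6.6.3 and 7.9 use the Safety Analysis Set for the placebo-controlled period and the Extension Analysis Set for the extension. SAP 7.9.2 lists all AEs but summarises only TEAEs.

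**The concern.** Two sections define an event as a TEAE that must be tabulated, and a third gives it no period to be tabulated in. The first-dose date matters most, because same-day reactions are the ones with the closest temporal link to dosing.

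By Protocol 6.3 and Table 3, Day 1 carries two injections, against one on each of Days 29, 57 and 85. That is 2 of 2 + 1 + 1 + 1 = 5 injections in the placebo-controlled period, or 40%. In Arm 1 it is also 400 of 400 + 3 × 200 = 1,000 mg. Protocol Table 2 asks for 30 minutes of observation after each dose.

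AE incidence is the secondary safety endpoint (Protocol 3.2). The Week 16 analysis tabulates AEs to inform the sponsor's development decisions (SAP 3.4), and there is no data and safety monitoring board (Protocol 10.1.6). If acute reactions were more frequent on imsidolimab, omitting them from the placebo-controlled summary would shrink the difference from placebo.

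**Working it through.** The SAP states no figure on this point, so the check applies the rule as written to each kind of onset.

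**Inputs**

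- P1 = AP01SDT, taken as the first-dose date, Study Day 1 (assumption; Appendix 1, item 5, sets the first-dose day to Study Day 1).
- P2 = AP02SDT, taken as the Week 16 dose date, nominal Day 113 (assumption; SAP 3.1 starts the extension at that dose).
- x = AESTDTC in study days. The range runs to Day 286, the end of the Week 40 window in SAP Table 2.
- A missing value sorts below every number, as in SAS (assumption).

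**Rule as written:** placebo-controlled if P1 < x; otherwise extension and follow-up if P2 < x; otherwise no period.

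**Comparison by date**

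| Onset x | As written | Only < changed to <= | P1 <= x < P2, then x >= P2 |
|---|---|---|---|
| Day 1 | Neither (1 < 1 false; 113 < 1 false) | Placebo-controlled | Placebo-controlled |
| Day 2 | Placebo-controlled (1 < 2) | Placebo-controlled | Placebo-controlled |
| Day 112 | Placebo-controlled | Placebo-controlled | Placebo-controlled |
| Day 113 | Placebo-controlled | Placebo-controlled | Extension and follow-up |
| Day 281 | Placebo-controlled | Placebo-controlled | Extension and follow-up |
| Missing | Neither | Neither | Needs its own rule |
| Baseline AE dated Day -5, later worse | Neither | Neither | Needs the worsening date |

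Over Days 1 to 286 the written rule puts 285 days in the placebo-controlled period, 1 day (Day 1) in neither, and none in the extension. The second test can never succeed: if P1 < x is false, then x <= P1 <= P2, so P2 < x is false too. That is the missing upper bound in the same line.

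**Comparison by clock time** (illustrative dose at 10:00, so P1 = 1 + 10/24 = 1.417 and P2 = 113.417)

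- Onset at 14:00: x = 1 + 14/24 = 1.583. Since 1.417 < 1.583, the event is placebo-controlled.
- Onset time unknown, taken as start of day: x = 1.000. Both 1.417 < 1.000 and 113.417 < 1.000 are false, so the event is in neither period.
- Onset time equal to dose time: x = P1, and the strict test fails.

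**Two separate causes.** The strict sign explains the Day 1 loss on the date reading. It does not explain the missing-date or worsened-baseline losses, which persist with <=. Those arise because the rule has no provision for such events.

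**The case against.** The strongest reply is that the comparison may be by clock time. SAP 6.6.3 compares AE onset with the time of the first dose, and Appendix 1, item 2, takes date and time of first dose from the Dosing eCRF. A reader might infer from the strict sign that every first-dose-date TEAE is lost. The documents do not support that without the condition that the comparison is by date. What remains on the clock-time reading is the event with unknown onset time, which SAP 6.6.3 expressly counts as a TEAE, and the event timed exactly at the dose.

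A reader might also blame the strict sign for the loss of undated events. It is not the cause: they fail under <= as well.

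Next, the intent to tabulate all TEAEs is stated, and a programmer may notice the gap. That is fair, but the statement of intent contradicts the rule without naming a period for these events.

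It is also tempting to say that events vanish from the report, or to put a number of subjects on the loss. Neither is supported. All AEs are listed (SAP 7.9.2), and the documents give no rate of first-day reactions. Subjects are counted once per preferred term, so one with the same term later in the period still counts. The summaries are descriptive, and no efficacy result changes.

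Finally, the missing upper bound in the same line is the larger defect. That is right, and both should be corrected together. Adding only the upper bound would leave the events described here without a period.

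**Conclusion.** The rule is wrong as written and conflicts with SAP 6.6.3. If AP01SDT and AP02SDT are period start dates compared by date, every TEAE with onset on the first-dose date enters neither period table. If clock times are compared, the loss narrows to first-dose-date events with unknown time (taken as start of day) or a time equal to the dose time. On either reading, a TEAE with a completely missing start date, or a baseline AE that worsens but keeps its pre-dose start date, also has no period, for lack of a rule rather than because of the sign. The effect is confined to the by-period TEAE summaries. The number of events cannot be estimated from the documents.

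**What to change.** Rewrite the period assignment in Appendix 1, item 8, once, together with the missing upper bound:

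1. Define AP01SDT and AP02SDT, and state whether dates or date-times are compared.
2. Placebo-controlled period: AP01SDT <= onset < AP02SDT, or AP01SDT <= onset if no extension dose was given. Extension and follow-up: onset >= AP02SDT.
3. On a dose date that opens a period, compare onset time with dose time, and state a default for unknown times. For the first-dose date that default is the placebo-controlled period, consistent with SAP 6.6.3. The Week 16 dose date needs its own stated default.
4. For a baseline AE that worsens, use the date of worsening as the onset.
5. State a default period for undated TEAEs. It should use any partial start date or the end date, and it should not credit to placebo an event that may have begun on imsidolimab. Sending all undated events to the placebo-controlled period would do that for Arm 3 subjects who went on to an extension dose. One workable form for those subjects is to assign the event to extension and follow-up unless a partial start date or the end date places it earlier.

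The cost is one revised SAP entry and the matching program. No new data are needed, provided the date of worsening is available from the severity changes that Protocol 8.2.1.4 already requires to be documented.
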